9.8 Adverse Events of Special Interest

Adverse events of special interest are events that Janssen Scientific Affairs, LLC is actively monitoring as a result of a previously identified signal (even if non-serious). These adverse events are:

- Infusion reactions: \geq grade 3
- Infections: \geq grade 4
- Cytopenias: \geq grade 4
- HBV Reactivation
- Other malignancies

Any Adverse Event of Special Interest that is to be reported to the COMPANY should be recorded on a Serious Adverse Event Report Form and be reported to the COMPANY **within 24 hours of knowledge of the event.**

9.9 Expedited Reporting to Hospital Risk Management

Participating investigators will report to their local Risk Management office any participant safety reports or sentinel events that require reporting according to institutional policy.

9.10 Routine Adverse Event Reporting

All Adverse Events must be reported in routine study data submissions to the Overall PI on the toxicity case report forms. AEs reported through expedited processes (e.g., reported to the IRB, FDA, etc.) must also be reported in routine study data submissions.

9.11 Unlisted (Unexpected) Adverse Event/Reference Safety Information

An adverse event is considered unlisted if the nature or severity is not consistent with the applicable product reference safety information. For a medicinal product(s) with a marketing authorization, the expectedness of an adverse event will be determined by whether or not it is listed in the applicable product information.

<http://www.darzalex.com/shared/product/darzalex/darzalex-prescribing-information.pdf>

For DARZALEX® (daratumumab), the expectedness of an adverse event will be determined by whether or not it is listed in the Investigator's Brochure

9.12 Special Reporting Situations

CONFIDENTIAL

This document is confidential. Do not disclose or use except as authorized.

Safety events of interest for a Janssen medicinal product that require expediting reporting and/or safety evaluation include, but are not limited to:

- Drug exposure during pregnancy (maternal and paternal)
- Overdose of a Janssen medicinal product
- Exposure to a Janssen medicinal product from breastfeeding
- Suspected abuse/misuse of a Janssen medicinal product
- Inadvertent or accidental exposure to a Janssen medicinal product
- Any failure of expected pharmacological action (i.e., lack of effect) of a Janssen medicinal product
- Medication error involving a Janssen medicinal product (with or without patient exposure to the Janssen medicinal product, e.g., name confusion)
- Suspected transmission of any infectious agent via administration of a medicinal product
- Unexpected therapeutic or clinical benefit from use of a Janssen medicinal product

These safety events may not meet the definition of an adverse event; however, from a Janssen Scientific Affairs, LLC perspective, they are treated in the same manner as adverse events. Special situations should be recorded on the Adverse Event page of the CRF.

Any special situation that meets the criteria of a serious adverse event should be recorded on a Serious Adverse Event Report Form and be reported to Janssen Scientific Affairs, LLC **within 24 hours of becoming aware of the event.**

9.13 SAEs, Adverse Events of Special Interest and Special Reporting Situations

All serious adverse events that have not resolved by the end of the study, or that have not resolved upon discontinuation of the subject's participation in the study, must be followed until any of the following occurs:

- The event resolves
- The event stabilizes
- The event returns to baseline, if a baseline value/status is available
- The event can be attributed to agents other than the study drug or to factors unrelated to study conduct
- It becomes unlikely that any additional information can be obtained (subject or health care practitioner refusal to provide additional information, lost to follow-up after demonstration of due diligence with follow-up efforts)

The coordinating center will transmit all SAEs, Adverse Events of Special Interest and special situations following exposure to a Janssen product under study in a form provided by Janssen Scientific Affairs, LLC in accordance with Section 9.7, Expedited Reporting to Janssen, in English **within 24-hours of becoming aware of the event(s).**

In the event the study is blinded, the coordinating center will submit an unblinded SAE or pregnancy exposure report to Janssen Scientific Affairs, LLC.

All follow-up information for serious adverse events that are not resolved at the end of the study or by the time of patient withdrawal must be reported directly by the coordinating center, **within 24 hours becoming aware,** to Janssen Scientific Affairs, LLC using the Janssen Scientific Affairs, LLC Serious Adverse Event Report

CONFIDENTIAL

This document is confidential. Do not disclose or use except as authorized.

All available clinical information relevant to the evaluation of a related SAE, Adverse Events of Special Interest, serious ADR or special situation is required.

- The coordinating center is responsible for ensuring that these cases are complete and if not are promptly followed-up. A safety report is not considered complete until all clinical details needed to interpret the case are received. Reporting of follow-up information should follow the same timeline as initial reports.
- Copies of any and all relevant correspondences with regulatory authorities and ethics committees regarding any and all serious adverse events, irrespective of association with the Janssen Product under study, are to be provided to Janssen Scientific Affairs, LLC using a transmission method in Section 9.7 within **24 hours of such report or correspondence being sent to applicable health authorities.**

9.14 Non-Serious AEs

All non-serious adverse events should be reported to Janssen Scientific Affairs, LLC according to the timeframe outlined in the Research Funding Agreement section entitled Reporting of Data.

9.15 Product Quality Complaint (PQC)

A product quality complaint is defined as any suspicion of a product defect related to a potential quality issue during manufacturing, packaging, release testing, stability monitoring, dose preparation, storage or distribution of the product, or delivery system. Not all PQCs involve a subject. Lot and batch numbers are of high significance and need to be collected whenever available.

Examples of PQC include but not limited to:

- Functional Problem: e.g., altered delivery rate in a controlled release product
- Physical Defect: e.g. abnormal odor, broken or crushed tablets/capsules
- Potential Dosing Device Malfunction: e.g., autoinjector button not working, needle detaching from syringe
- Suspected Contamination
- Suspected Counterfeit

A PQC may have an impact on the safety and efficacy of the product. Timely, accurate, and complete reporting and analysis of PQC information from studies are crucial for the protection of patients, investigators, and Janssen Scientific Affairs, LLC, and are mandated by regulatory agencies worldwide. Janssen Scientific Affairs, LLC has established procedures in conformity with regulatory requirements worldwide to ensure appropriate reporting of PQC information. Lot and/or Batch #s shall be collected for any reports of failure of expected pharmacological action (i.e., lack of effect). The product should be quarantined immediately and if possible, take a picture.

All initial PQCs involving a Janssen medicinal product under study must be reported to Janssen Scientific Affairs, LLC by the coordinating center within 24 hours after being made aware of the event. The Janssen contact will provide additional information/form to be completed.

CONFIDENTIAL

This document is confidential. Do not disclose or use except as authorized.

If the defect for a Janssen medicinal product under study is combined with either a serious adverse event or non-serious adverse event, the coordinating center must report the PQC to Janssen Scientific Affairs, LLC according to the serious adverse event reporting timelines. A sample of the suspected product should be maintained for further investigation if requested by Janssen Scientific Affairs, LLC.

9.16 Pregnancy

All initial reports of pregnancy must be reported to Janssen Scientific Affairs, LLC by the Overall Principal Investigator within 24 hours of becoming aware of the event using the Serious Adverse Event Form. Abnormal pregnancy outcomes (e.g. spontaneous abortion, fetal death, stillbirth, congenital anomaly, ectopic pregnancy) are considered serious adverse events and must be reported using the Serious Adverse Event Form.

Any subject who becomes pregnant during the study must be promptly withdrawn from the study and discontinue further study treatment.

Because the effect of the Janssen medicinal product on sperm is unknown, pregnancies in partners of male subjects exposed to a Janssen medicinal product will be reported by the Overall Principal Investigator within 24 hours of their knowledge of the event using the Serious Adverse Event Form. Depending on local legislation this may require prior consent of the partner.

Follow-up information regarding the outcome of the pregnancy and any postnatal sequelae in the infant will be required.

10. STUDY CALENDAR

Screening evaluations are to be conducted within 42 days prior to registration. Baseline assessments are to be conducted on C1D1 of initial therapy and should be considered separate from screening evaluations. If screening assessments are performed within 7 days of C1D1, disease assessments do not need to be repeated. All assessments must be performed prior to administration of any study medication. See below for detailed scheduled of assessments. Study medications will be administered according to the schedule and guidelines outlined in Section 5.

Tests and procedures	Pre-registration	During Treatment ^{1,3}			End of Treatment ¹³	Follow Up ¹⁸
	≤ 42 days prior to registration	Cycle 1-20 Day 1	Cycle 1-20 Intracycle on Days of Dosing	Clinically Indicated or to confirm CR ⁹		Every 3-6 Months ²²
History and exam, height, weight, vital signs. Performance Status	X	X			X	X
Toxicity Notation	X	X			X	
Hematology group (WBC w/ diff, PLT, Hgb, ANC) ^{1,10}	X	X	X		X	X
Chemistry ^{4, 10}	X	X	X		X	X
Direct & total bilirubin ^{2, 10}	X	X	X		X	
Blood Type and IAT Testing ¹⁴	X					

CONFIDENTIAL

This document is confidential. Do not disclose or use except as authorized.

HIV, HBV, HCV Testing ^{19,20}	X	X ²⁰			X ²⁰	X ²⁰
Free light chain assay ¹⁰	X	X			X	X
Serum and Urine Immunofixation (SPEP and UPEP) with quantitative immunoglobulins ^{10, 11}	X	X ⁸			X	X
Response Assessment ¹⁷		X			X	X
β2M, CRP, LDH ¹⁰	X	X	X		X	X
Metastatic Bone Survey and MRI of the Full Spine OR PET/CT ¹⁶	X				X	X
EKG	X				X	
PFT ²¹	X					
Serum or urine pregnancy test	X					
Unilateral bone marrow aspirate and biopsy ⁵	X			X	X	X ¹²
Research bone marrow aspirate ⁶	X ⁵			X ⁶	X ⁶	X ¹²
Research Blood ⁷	X ⁷	X ⁷		X ⁷	X ⁷	X
Research Buccal Swab ¹⁵	X					

- 1- Cycle 1, Day 1 hematologic laboratory values need to meet eligibility criteria to begin treatment
- 2- Direct bilirubin to be obtained if total bilirubin is abnormal.
- 3- Scheduling allows for -2/ +7 days.
- 4- Chemistry includes sodium, potassium, chloride, bicarbonate, blood urea nitrogen, creatinine, calcium, glucose, albumin, ALT (SGPT), total protein, AST (SGOT), total bilirubin, uric acid, alkaline phosphatase, magnesium, and phosphorus.
- 5- These procedures should also be done at any time during the course of the study to confirm CR, or as clinically indicated
- 6- Research bone marrow aspirate and biopsy at same time of clinically indicated bone marrow biopsy and to confirm response.
- 7- Peripheral blood samples for correlative studies.
- 8- SPEP with immunofixation and quantitative immunoglobulins should be performed at screening, cycles 1-20 day 1, EOT, and at each follow-up visit.
- 9- If confirmation of response BM biopsy/aspirate was performed within 12 weeks of subsequent time point listed; the aspirate need only be repeated.
- 10- For Cycle 1 Day 1, no need to repeat tests if they have been performed within the past 7 days. Testing may be performed up to 2 days before other infusion days. Results of hematology tests must be evaluated before each study drug administration. Perform at additional timepoints, as clinically indicated. To be done by local lab. Patients need only meet hematologic inclusion criteria to begin treatment on C1D1.
- 11- If the participant's disease response is not followed primarily via a UPEP and Urine immunofixation, these tests may be done only at screening, as clinically indicated during treatment, end of treatment, and as clinically indicated during follow-up.
- 12- Strongly recommended to be performed yearly after EOT during follow-up and is required when there is suspected clinical progression
- 13- End of Treatment Assessments should be performed 4 weeks (+/- 1 week) after the last dose of daratumumab
- 14- Participants should receive blood typing card per section 3.3.1, prior to first dose of therapy- If the participating institution does not have a card that it provides its patients, refer to Appendix G for a template for completion by the study team and given to each participant
- 15- Buccal swab(s) may be collected at any time during the study
- 16- If PET/CT results are concerning for myeloma involvement, a follow up MRI must be conducted to confirm eligibility (baseline) or progression (on study and in follow up) PET CT strongly recommended yearly after EOT during follow up and are required at time of suspected disease progression.
- 17- A response assessment is required starting on C2D1, and at cycle thereafter based on Day 1 values, at EOT, and at each follow up Day 1 until off study.
- 18- If travel to the main site is financially burdensome on the participant, an alternate follow up schedule may be approved after discussion with the Overall PI- Window for follow up visits is +/- 4 weeks (28 days)
- 19- Subjects who are currently in the treatment phase of the study who are within 6 months of starting study treatment when DFCl Protocol Amendment 11 is implemented will be required to have HBV serology performed locally upon signing the updated ICF- HBV serology and DNA testing is not required at screening or for subjects ongoing in the Treatment Phase who are within 6 months of starting study treatment if this was performed as part of standard of care within 3 months prior to first dose of daratumumab.
- 20- HBV testing for those with serologic evidence of resolved HBV infection (i.e., positive Anti-HBs or positive Anti-HBc)

CONFIDENTIAL

This document is confidential. Do not disclose or use except as authorized.

at Screening, HBV DNA testing by PCR must be performed locally every 12 weeks during treatment, at the End of Treatment Visit, and every 12 weeks for up to 6 months (24 weeks) after the last dose of study treatment- Refer to 5.2.1.5
21- Only those who are known to have COPD (chronic obstructive pulmonary disease) or severe, persistent asthma, or thought to have compromised lung function must have a PFT to confirm eligible (must have a FEV1 <50% of predicted normal.)
22- Participants unable to participate in follow up every 3 months may follow up every 6 months at PI discretion in accordance with standard of care follow-up frequency and COVID precautions. Physical exams and correlative blood draws that are not done due to virtual visits will not be considered violations. Local myeloma labs must be provided to the participating site for data entry purposes. Bone marrow biopsy and scans are strongly recommended yearly after EOT but are required when there is suspicion of clinical progression. These assessments can be waived due to extenuating circumstances or for insurance coverage reasons. Scans and bone marrow biopsy and research samples are required at time of suspected disease progression if one is performed

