3.2 Exclusion Criteria

- 3.2.1 Any prior therapy for symptomatic Multiple Myeloma or smoldering Multiple Myeloma should also be excluded, including prior use of IMiDs, proteasome inhibitors, or CD138 inhibitors. Prior therapy for smoldering Multiple Myeloma with agents that are not therapeutically active against MM is not an exclusion criterion. Other prior treatment may be allowed after discussion and approval by the overall PI.
- 3.2.2 Other concurrent chemotherapy, immunotherapy, radiotherapy, or any ancillary therapy considered investigational. Prior therapy with bisphosphonates is allowed. Prior radiation therapy to a solitary plasmacytoma is allowed.
- 3.2.3 Concurrent exposure to any commercially available agents known to be active against SMM and MM.
- 3.2.4 Serious medical or psychiatric illness likely to interfere with participation in this clinical study.
- 3.2.5 Diagnosed or treated for another malignancy within 2 years of enrollment, with the exception of complete resection of basal cell carcinoma or squamous cell carcinoma of the skin, an in situ malignancy, or low-risk prostate cancer after curative therapy.
- 3.2.6 Subject has known chronic obstructive pulmonary disease (COPD) or severe, persistent asthma with a Forced Expiratory Volume in 1 second (FEV1) < 50% of predicted normal.
 - Note that FEV1 testing is required at screening for patients suspected of having COPD or severe, persistent asthma and subjects must be excluded if FEV1 <50% of predicted normal.

CONFIDENTIAL

This document is confidential. Do not disclose or use except as authorized.

- 3.2.7 Subject has known moderate or severe persistent asthma within the past 2 years or currently has uncontrolled asthma of any classification.
- Subjects who currently have controlled intermittent asthma or controlled mild persistent asthma are allowed in the study
- 3.2.8 Uncontrolled intercurrent illness including, but not limited to, ongoing or active infection, symptomatic congestive heart failure, unstable angina pectoris, uncontrollable cardiac arrhythmia, or psychiatric illness/social situations that would limit compliance with study requirements.
- 3.2.9 Pregnant or nursing women will be excluded from the study.
- 3.2.10 History of allergic reactions attributed to compounds of similar chemical or biologic composition to Daratumumab.

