4. REGISTRATION PROCEDURES

4.1 General Guidelines for DF/HCC and DF/PCC Institutions

Institutions will register eligible participants in the Clinical Trials Management System (CTMS)

CONFIDENTIAL

This document is confidential. Do not disclose or use except as authorized.

OnCore. Registrations must occur prior to the initiation of protocol therapy. Any participant not registered to the protocol before protocol therapy begins will be considered ineligible and registration will be denied.

An investigator will confirm eligibility criteria and a member of the study team will complete the protocol-specific eligibility checklist.

Following registration, participants may begin protocol therapy. Issues that would cause treatment delays should be discussed with the Overall Principal Investigator (PI). If a participant does not receive protocol therapy following registration, the participant's registration on the study must be canceled. Registration cancellations must be made in OnCore as soon as possible.

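### Study Calendar footnote 21 makes FEV1 below 50% of predicted a condition of eligibility, while exclusion 3.2.6 makes the same finding a reason to exclude

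*Combined protocol and SAP*

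**What the plan says.** Criterion 3.2.6 (Section 3.2, Exclusion Criteria) lists as an exclusion known COPD or severe, persistent asthma "with a Forced Expiratory Volume in 1 second (FEV1) < 50% of predicted normal". A note beneath it does two things. It states who is tested: "FEV1 testing is required at screening for patients suspected of having COPD or severe, persistent asthma". It then states the consequence: "subjects must be excluded if FEV1 <50% of predicted normal".

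The Study Calendar in Section 10 has a PFT row that is marked only in the pre-registration column and carries footnote 21. The section opens with the timing rule "Screening evaluations are to be conducted within 42 days prior to registration". Footnote 21 limits the test to patients known to have COPD or severe, persistent asthma, "or thought to have compromised lung function must have a PFT". For that group it says they "must have a PFT to confirm eligible (must have a FEV1 <50% of predicted normal".

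Criterion 3.2.7 is also relevant. It excludes on asthma history without reference to FEV1: "Subject has known moderate or severe persistent asthma within the past 2 years".

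**The concern.** Footnote 21 exists only to govern a screening test, so it is an operative eligibility instruction. Read as printed, it requires the finding that 3.2.6 says must lead to exclusion. A site working from the calendar alone could enrol a patient with COPD whom 3.2.6 excludes, or turn away one whom 3.2.6 does not exclude.

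The criterion appears to serve safety, although the documents support that link only indirectly. Sections 2.6.6 and 9.2.1.1 report bronchospasm in 10 subjects across all ongoing daratumumab studies, most of them with underlying respiratory disease, and give no rate by FEV1. Section 5.2.1.3 sets extra post-infusion precautions for subjects with FEV1 below 80% or with asthma, and mentions control medication for subjects with COPD. The protocol therefore expects some enrolled patients to have impaired lung function, and the rule could matter in practice.

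**Working it through.** The plan has no figure to reproduce here. The check is a comparison of the two passages for a patient with known COPD, who falls under both.

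| FEV1 (% of predicted) | Footnote 21, as printed | Criterion 3.2.6 and its note |
|---|---|---|
| below 50 | meets the stated condition | must be excluded |
| 50 or above | does not meet the stated condition | not excluded on FEV1 |

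1. Footnote 21 admits the set {FEV1 < 50}.
2. Criterion 3.2.6 with its note leaves unexcluded, at most, the set {FEV1 ≥ 50}.
3. The intersection of {FEV1 < 50} and {FEV1 ≥ 50} is empty, so no value satisfies both.

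**Does another reading of 3.2.6 remove the conflict?** The sentence can be parsed in two ways. The FEV1 limit may apply to both COPD and severe asthma, or only to asthma, in which case all known COPD is excluded. Under the first reading step 2 stands. Under the second, no FEV1 value makes a patient with COPD acceptable to 3.2.6, and the intersection is still empty. The conflict survives either way.

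**Which patients does it reach?** Known moderate or severe persistent asthma within the past 2 years is excluded by 3.2.7 whatever the FEV1. The practical conflict therefore falls mainly on COPD.

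**Do the two passages test the same group?** Not exactly. The note to 3.2.6 names patients suspected of COPD or severe, persistent asthma. Footnote 21 names those known to have these conditions and adds those thought to have compromised lung function. The groups overlap and the practical difference is small, but a single amendment should align them.

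**Could the rule still be in use?** Section 15.2 plans 2 years of accrual. Appendix E, Section 1.2, plans 25 months (50 patients ÷ 2 per month = 25). The Appendix D cover carries a version date of 26 July 2021. None of these says whether screening is open.

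**The case against.** The strongest reply is that the structure of the protocol already shows which text governs. Eligibility criteria sit in Section 3. Appendix D, Section 3.8.2, defines an exception by reference to the inclusion and exclusion criteria, and Section 3.7.3 allows none without IRB approval. The calendar is a schedule of assessments, and its footnote speaks of confirming eligibility, which points back to criteria set elsewhere. Section 3.2.6 also states its threshold twice. On this view the footnote is a one-symbol drafting slip that no careful site would follow.

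Several layers of checking also exist. Under Section 4.1 an investigator confirms eligibility and "a member of the study team will complete the protocol-specific eligibility checklist". Outside sites have central verification (Section 4.4; Appendix D, Section 3.7.1). Participating Institutions have an eligibility review within 30 days of enrolment (Appendix D, Section 5.1). Nothing in the documents suggests that anyone has been wrongly enrolled.

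Finally, the point turns on one comparison sign, and signs are visibly damaged elsewhere, for example in the focal-lesion line of Table 1 and the lead-in to the criteria in Section 13.1.

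Much of this stands as mitigation. A slip is plausible and the safeguards lower the chance of harm. They do not remove the conflict, because no clause expressly gives one passage precedence. The safeguards check patients against the protocol, and here the protocol states two opposite rules. The checklist that would settle the matter at site level is not in the documents, and the 30-day review comes after enrolment. Nothing indicates that the sign in footnote 21 is itself misprinted, although confirming it against the sponsor's master copy takes a moment.

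**Conclusion.** The concern holds. As written, footnote 21 and criterion 3.2.6 contradict each other, and for a patient with COPD covered by both there is no FEV1 value that meets both.

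Its size in patients is unknown: the documents give neither the number needing a PFT nor the distribution of FEV1. It has no bearing on the sample size of 50, the power statement, or the rule that at least 32 of 50 deep responses is promising. It should be fixed because it is a reversed screening instruction with an apparent safety purpose, but it does not threaten the primary analysis.

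The conclusion rests on the printed wording of both passages being what sites hold. It takes no position on which rule is the right one; that is for the sponsor to state. If accrual has closed, which is an assumption, the remaining practical value lies in checking the records already collected.

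**What to change.** The sponsor should reconcile criterion 3.2.6 and Study Calendar footnote 21 so that the FEV1 condition and the group to be tested read the same in both places, and should make clear whether the FEV1 limit in 3.2.6 applies to COPD as well as to asthma. It should then confirm that the eligibility checklist carries the reconciled wording, notify sites if screening is still open, and compare existing screening PFT records with the reconciled criterion to see whether anyone was enrolled or refused on the wrong reading.

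The cost is a short wording correction in the next amendment, a checklist check, possibly one site notice, and a review of the screening PFT records. For Participating Institutions that review can build on the eligibility review already required by Appendix D, Section 5.1.

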8.4 Duration of Follow Up

Participants will be followed every 3 or 6 months (+/-28 days) for up to 5 years after end of treatment. We plan to capture progression free survival, second progression free survival as well as time to biochemical progression, and time to progression to active symptomatic MM and any subsequent therapies for MGUS, SMM or MM. . If travel to the main site is financially burdensome for the participant during maintenance, an alternate schedule may be approved after discussion with the Overall PI.

Participants unable to participate in follow up every 3 months may follow up every 6 months at PI discretion in accordance with standard of care follow-up frequency and COVID precautions. Physical exams and correlative blood draws that are not done due to virtual visits will not be considered violations. Local myeloma labs must be provided to the participating site for data entry purposes. Bone marrow biopsy and scans are strongly recommended yearly after EOT, but not require however, scans and bone marrow biopsy and research samples are required at time of suspected disease progression

The following is required during the Active Follow Up period (for up to 5 years):

1. Physical exams are voluntary during this period
 - a. Virtual visits/telehealth visits are acceptable
2. SPEP and Immunofixation
3. Serum Free Light Chains (SFLC)
4. UPEP and Immunofixation only for those where disease is tracked by the urine
5. Serum Immunoglobulin test
6. PET/CT assessments are strongly recommended yearly and is required at the time of suspected progression
 - a. The same assessment modality should be used consistently across the duration of the trial

CONFIDENTIAL

This document is confidential. Do not disclose or use except as authorized.

7. Bone marrow biopsies are and strongly recommended yearly after EOT and is required at the time of suspected progression
8. Research bone marrow samples will be collected at the time of any bone marrow biopsy/aspirate procedure
9. Research blood will be collected whenever an in person visit to the site occurs. Research blood samples that are not collected at time points in the collection calendar due to COVID precautions or q6 month follow up will not be considered violations unless it is missed at the time of suspected progression.
10. Response
11. CRAB/MDE Assessment
12. Bone marrow biopsy/aspirate results and cytogenetics/FISH if ordered
13. Scan results and modality

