13.2.4 Duration of Response and Endpoint Definitions

Duration of overall response: The duration of overall response is measured as the time from initiation of first response to first documentation of disease progression or death. Patients who have not progressed or died are censored at the date last known progression-free.

Duration of overall complete response: The duration of overall CR is progression or death. Patients who have not progressed or died are censored at the date last known progression-free.

Time to progression: Time to progression is defined as the time of randomization until progression. Patients who have died without evidence of progression are censored in the TTP analysis at the time of death and patients who are alive without progression are censored at the last disease assessment.

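### Footnote 22 of the study calendar lets the work-up at suspected progression be waived, against Section 8.4 and footnotes 12 and 16, so progression visible only on imaging or marrow can be censored

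*Combined protocol and SAP*

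**What the plan says.** Four places set the rule for the work-up at suspected progression during follow-up.

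- **Section 8.4, text:** yearly marrow and scans are recommended but not required; at suspected progression, "scans and bone marrow biopsy and research samples are required at time of suspected disease progression". The numbered list repeats this for imaging (item 6: "PET/CT assessments are strongly recommended yearly and is required at the time of suspected progression") and for marrow (item 7). No waiver is given.
- **Calendar footnote 12 (marrow):** it "is required when there is suspected clinical progression". No waiver.
- **Calendar footnote 16 (imaging):** PET/CT scans "are required at time of suspected disease progression", and a worrying PET/CT must be followed by MRI to confirm progression. No waiver.
- **Calendar footnote 22 (follow-up column):** "Bone marrow biopsy and scans are strongly recommended yearly after EOT but are required when there is suspicion of clinical progression". The next sentence reads "These assessments can be waived due to extenuating circumstances or for insurance coverage reasons". The footnote ends: "Scans and bone marrow biopsy and research samples are required at time of suspected disease progression if one is performed".

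For duration of response, Section 13.2.4 says: "Patients who have not progressed or died are censored at the date last known progression-free". Section 13.2.5 applies the same rule to PFS. Neither says how to treat a progression that was suspected but not worked up. Section 13.2.6 plans no central review. Section 15.1.2 plans a Kaplan-Meier analysis of duration of response.

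**The concern.** A site can comply with footnote 22 and breach Section 8.4. If it uses the waiver, a patient in whom progression is suspected may have no scan or marrow, and so no documented event. Under the censoring rules that patient can be counted as progression-free.

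The censoring would then be informative: it would fall on patients selected because their disease appeared to be progressing, and for a reason, such as insurance coverage, that has nothing to do with that disease. At stake is duration of response, a secondary endpoint, together with PFS and time to symptomatic myeloma, which Section 8.4 says will be captured. The correlative work on progression could also lose marrow samples at that time point.

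**Working it through.** **1. Does this touch the primary design?** The plan's only design figures are in Section 15.1: 50 patients, promising if at least 32 respond, type I error 0.03, power 86% and 97%. Exact binomial tails reproduce them:

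- P(X ≥ 32 | n = 50, p = 0.50) = 0.0325
- P(X ≥ 32 | n = 50, p = 0.70) = 0.859
- P(X ≥ 32 | n = 50, p = 0.75) = 0.971

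The 90% exact lower limit is 0.514 for 32/50 and 0.494 for 31/50, so the cut-off of 32 is right. None of this depends on footnote 22. The waiver belongs to the follow-up column, and VGPR is defined on M-protein (or on free light chains where only these are measurable).

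**2. Is the conflict real?** Section 8.4 and footnotes 12 and 16 are unconditional. In footnote 22 the waiver directly follows a sentence that covers both the yearly tests and those required on suspicion, so its plain reference is to both. The last sentence weakens the requirement again, because it applies only where a procedure takes place.

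**3. Which progressions are exposed?**

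| Route to progression | Source | Still captured if the work-up is waived? |
|---|---|---|
| Rise in serum M-protein, or in urine M-protein where disease is tracked in urine | 13.2.2.1; tests required by 8.4 | Yes |
| Rise in involved minus uninvolved free light chains; abnormal ratio | 13.2.2.1, 13.1; test required by 8.4 | Yes |
| Calcium, renal function, anemia | 13.1; CRAB/MDE assessment required by 8.4, blood counts and chemistry in the calendar | Yes |
| New or larger bone lesions, focal lesions | 13.1, 13.2.2.1 | Not without imaging |
| Soft tissue plasmacytomas | 13.2.2.1 | Not reliably without imaging |
| Marrow plasma-cell percentage as a myeloma-defining event | 13.1 | Not without marrow |
| Marrow increase as progressive disease | 13.2.2.1, only without measurable M-protein or free light chains | Not without marrow |

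The exposure is the last four rows, in patients who meet no laboratory criterion at the same time.

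**4. Which way does the error go?** Take a true progression that is not verified. If the patient is censored at the last clean visit, the event is lost and a high-risk patient leaves the risk set. If the patient stays at risk, the event is dated late or never. Both raise the estimated curve.

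**5. Can it be sized?** The loss is the product of two shares: progressions visible only on imaging or marrow, and those among them whose work-up is waived and never made up. The documents give neither.

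**The case against.** The best defense is that footnote 22 is loosely drafted rather than contradictory. The waiver may be meant for the yearly tests only, since the requirement at suspected progression is restated after it. The closing condition may refer to research samples, in line with Section 8.4 item 8, which collects research marrow at any marrow procedure. This reading is possible but weak: a test that is only recommended needs no waiver, and the sentence before the waiver includes the required tests. Section 8.4 item 9 also excuses missed research blood except at suspected progression, which suggests that this is the visit the protocol meant to protect.

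The objection to the consequence is stronger, and much of it stands. A reader might infer that any suspected progression without a work-up is counted as no progression. The documents do not support that, because the laboratory routes remain open. Assessments also recur every 3 to 6 months for up to 5 years, so some events would be found late rather than missed.

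A reader might also want a number. Take the 25% five-year rate for one-factor smoldering myeloma in Section 2.1 and assume that a share w of all progressions is lost. The observed rate is then 1 − 0.75^(1−w): 22.8%, 20.6% and 18.2% for w = 10%, 20% and 30%. This is not an estimate of the bias. It applies the loss to progressions that laboratory tests would detect, treats late events as lost, uses an untreated rate for a mixed population, and is not the Kaplan-Meier duration of response among responders.

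**Conclusion.** The inconsistency is in the current text and should be resolved. Its effect is narrow. Progression shown only by imaging or marrow can go unverified and be censored as progression-free. That can bias the Kaplan-Meier duration of response in the favorable direction. The same holds for PFS and time to symptomatic myeloma if they are reported; Section 15 plans no analysis of either, so it would go too far to say that all three planned estimates are biased. The primary endpoint and its power are essentially unaffected.

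The documents do not allow the bias to be sized. The conclusion assumes only that some sites would use the waiver at suspected progression and that some of the suspicions are true. A reader might infer that the waiver itself must go. The documents show that the passages disagree; they do not settle which rule should prevail.

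**What to change.** 1. Reconcile footnote 22 with Section 8.4 and footnotes 12 and 16, so that one rule states whether the waiver covers only the yearly assessments or also the work-up at suspected progression. Clarify what the closing condition of footnote 22 refers to. The choice is the sponsor's.
2. Whenever the work-up at suspected progression is not done, record the date of suspicion and the reason on the CRF. This is useful whichever rule is kept.
3. Add one sensitivity analysis of duration of response, and of PFS and time to symptomatic myeloma if reported, that counts each unverified suspected progression as an event on the date of suspicion. Present it as a bound, because some suspicions will be false and the date rests on the investigator's judgment.

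Cost: a text edit, a short CRF entry and one extra analysis. If the waiver is narrowed, some sites may log deviations, and some patients may meet coverage problems for scans or marrow.
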